## Project Abstract

Infertility affects 12% of couples in the United States. In vitro fertilization (IVF) is the most advanced treatment for infertility. Despite decades of improvements in hormonal drug therapy and laboratory techniques, IVF embryos continue to have low implantation potential (~30%/embryo). Therefore, it is not uncommon to transfer multiple embryos to the uterus in order to enhance success. As a result, approximately 30% of IVF pregnancies result in multiple gestation, which lead to higher morbidity and mortality of the mothers and infants. The best method to reduce multiple birth and associated morbidity and mortality is to transfer a single embryo with enhanced implantation potential. A recent meta-analysis of acupuncture for IVF showed it may augment IVF success by ~10%, although the underlying mechanism remains unclear. We hypothesize that acupuncture enhances IVF success by enhancing the perfusion of pelvic organs including the ovaries and the uterus. Since undergoing IVF treatment is a stressful process to most patients, we further hypothesize that acupuncture stabilizes the mind-body interaction by optimizing the psychological well-being of patients receiving IVF treatment.

Experimental Approach: (1) Participants: Women (ages 21 to 42) who seek IVF treatment at the Center for Fertility & Reproductive Surgery will be eligible for the study. Seventy women will be recruited and randomly assigned to either the intervention (acupuncture plus standard care) or the comparison (standard care alone) group. (2) Intervention: Participants in the intervention group will receive 3 acupuncture sessions during the project with the first treatment between day 6–8 of the stimulated IVF cycle, second treatment on the day of embryo transfer and the third treatment post-transfer, within 48 hours. Participants in the comparison group will receive no intervention but will receive standard care. (3) Measures: The primary outcome measures include prostacyclin and thromboxane vasoactive biomarkers. Secondary outcome measures include perceived stress levels. (4) Procedure: Upon IRB approval, an informed consent will be provided to all participants. Pre- and post- acupuncture urinary metabolites of prostacyclin and thromboxane will be assessed. A standardized Perceived Stress Scale will be administered before each acupuncture session for the study group, and before a 30-40-minute waiting period for the control group.

## ***Background and Significance***

Infertility affects approximately 1 in 8 couples (6.7 million women) in the United States (<http://www.cdc.gov/nchs/fastats/infertility>). Treatment for infertility is often expensive, time-consuming and stressful for the patient and her family. IVF is the most effective treatment for infertility, as it brings the oocytes and sperm together directly, provides an ideal early environment for embryo development and bypasses female infertility factors such as tubal occlusion, endometriosis and pelvic adhesions. However, the cost of IVF is often a limiting factor for families, especially noting that only 30% of embryos will successfully implant and result in pregnancy. Transferring multiple embryos may contribute to a higher chance of success, but this is complicated by a higher chance of multiple births (Pandian 2009). Multiple gestation poses a higher risk to both the mother and her pregnancy.

Despite advancements in embryo culture media, incubation systems and improved embryo transfer techniques, implantation of embryos is not always achieved. Therefore, women often seek alternative treatments to enhance their reproductive potential to maximize their chance of success. A recent meta-analysis of acupuncture for IVF showed improved success by ~10%, although the underlying mechanism remains unclear (Manheimer 2008).

Optimal blood supply to the uterus and ovaries are essential to the development of oocytes and the timely maturation of the uterine lining in preparation for embryo implantation. Enhancing perfusion of the pelvic organs is likely to result in improved clinical outcomes. The blood perfusion to organs is determined by local vascular tones, which in turn is controlled by the balance of two key vasoactive molecules, prostacyclin and thromboxane. The former relaxes the vascular smooth muscle, dilates blood vessels, and prevents platelet aggregation; the latter contracts the vascular smooth muscle, constricts blood vessels, and promotes platelets aggregation. Both thromboxane and prostacyclin are unstable: the former's half-life is 37 seconds and that of the latter is 60 minutes. Their urinary metabolites, thromboxane B2 (TBX2), and 2, 3-dinor-TXB2 (both from thromboxane), and 6-keto-prostaglandin F1 alpha (6-keto PGF1α), and 2, 3-dinor-6-keto-PGF1α (both from prostacyclin) are very stable. The concentrations of these metabolites are fairly easily determined using commercially available EIA assay kits.

Acupuncture is a traditional Chinese medicine therapeutic approach involving the insertion and manipulation of needles in the body to stimulate specific points. In an overview of the use of acupuncture in gynecology, Napadow (2008) and colleagues stated that recent basic and clinical research has demonstrated that acupuncture regulates uterine and ovarian blood flow, and that the effect is most likely mediated as a reflex response via the ovarian sympathetic nerves, and that the response is controlled via the supraspinal pathways. Additionally, Al-Inany (2008) suggested acupuncture may stimulate the production of endogenous opioids, which may inhibit the central nervous system's outflow and the biological stress response.

Stress is known to have a negative effect on reproduction and perhaps the menstrual cycle, and often negatively affects success of fertility treatment. Acupuncture has been found to reduce stress by activating endogenous opioids and blocking stress-induced elevations of HPA hormones. A recent meta-analysis by the National Institutes of Health, Division of Complementary and Alternative Medicine (NIHCAM) showed acupuncture enhances in vitro fertilization (IVF) success by approximately 10%. A recent meta-analysis results showed that the pooled clinical pregnancy rate from all of the acupuncture groups was significantly higher than that from all of the control groups (P=0.04) (Zheng, 2012). Six systematic reviews (including five meta-analyses) have shown that acupuncture on the day of embryo transfer (ET) has improved pregnancy rates in IVF (Kang, 2011). None of the reviews call for a rejection of this intervention and all, in fact, call for more exploration of its value to enhance IVF cycles.

It is not clear how the benefit is attained. Thus we further hypothesize that acupuncture stabilizes the mind-body interaction by optimizing the psychological well-being of patients receiving IVF treatment.

## **Project Narrative**

### ***Hypothesis and Specific Aims***

TEXAS TECH UNIVERSITY HEALTH SCIENCES CENTER

IRB NUMBER: L15-117

IRB APPROVAL DATE: 07/15/2019

Version 1.8/Date 7.12.2019

The purpose of this pilot study is to determine if acupuncture affects the vasoactive molecules (prostacyclin and thromboxane) in women undergoing IVF therapy. The investigators' overall hypotheses for this area of study, to be addressed with future research, are: (1) acupuncture augments IVF success by enhancing the perfusion of pelvic organs including the ovaries and the uterus, and (2) acupuncture reduces the levels of stress and optimizes mind-body interaction in individuals undergoing IVF.

### **Specific Aims:**

- (1) To measure the effects of acupuncture on key vasoactive urine molecules, i.e. prostacyclin and thromboxane, before and after acupuncture, and
- (2) to assess the impacts of acupuncture on the psychological well-being of women undergoing IVF treatment.

### **SIGNIFICANCE OF THE STUDY**

Results from the investigators' study will shed light on the mechanism by which acupuncture improves IVF outcomes. This may lead to other treatment strategies to improve success. Likewise, an established mechanism by which acupuncture improves IVF may lead to greater acceptance of this non-conventional treatment modality by the general population.

### ***Research Design and Methods***

This is a prospective, randomized, controlled study. Participants will be women in the Principal Investigator's practice seeking IVF. Participants will be randomized 1:1 into either the acupuncture group or the standard of care (no acupuncture) group. Each group will have 3 study visits during their 8-week IVF cycle.

#### **Rationale for the Control Group:**

A sham control group is not used because systematic review suggested that sham acupuncture controls may unnecessarily complicate the RCT evidence base given the nature of objective outcomes in IVF study (<http://www.ncbi.nlm.nih.gov/pmc/articles/PMC3124624/>).

#### ***Power analysis***

With 35 patients allocated to each group, assuming the Student's T-test will be used to determine the differences between two independent samples, effect sizes  $d \geq 0.6$  will be found statistically significant with alpha .05 and power .80. In practical terms, since the PSS validation samples showed a mean about 13.5 with variance=6.2, only averaged differences greater than 1.5 raw score points in PSS will be found statistically significant.

We plan to seek extramural funding in the future. We will use the data obtained from this pilot study to perform power analysis and to calculate the number of participants needed in future proposals.

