#### *Removal from study*

In the event that embryo growth does not progress or implantation is cancelled for any reason, the subject's participation in this study will end.

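### The stated power of 0.80 needs all 35 women per group, but the plan removes some women before visits 2 and 3 and makes no allowance for it

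*Combined protocol and SAP*

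**What the plan says.** All references are to the combined protocol and SAP.

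- **Sample size.** The Project Abstract says "Seventy women will be recruited and randomly assigned", and Research Design and Methods says "Participants will be randomized 1:1 into either the acupuncture group or the standard of care". That gives 35 per group.
- **Power.** The Power analysis section starts from "With 35 patients allocated to each group", "assuming the Student's T-test will be used to determine the differences between two independent samples", and says that effects of d = 0.6 or more "will be found statistically significant with alpha .05 and power .80". It does not state the sidedness, the visit or a loss rate.
- **Visits.** Under the Acupuncture Protocol and Control Group sections, visit 1 is on days 6 to 8 of the cycle, visit 2 is on transfer day before transfer, and visit 3 is after transfer.
- **Removal.** Removal from study opens "In the event that embryo growth does not progress or implantation is cancelled for any reason" and then ends the woman's participation. Control Group repeats the rule and says that such women are sent their vouchers after visit 1, so the plan expects women who have visit 1 only.
- **Partial offsets.** Poor Response to Egg Retrieval lets poor responders who plan a later retrieval stay in under the same randomisation and do visits 1 to 3 in a later cycle. The Perceived Stress Scale (PSS) section keeps the post-treatment questionnaire when transfer is postponed, at 3 to 7 days after retrieval. It has no matching provision for urine.
- **Surplus.** Recruitment and Projected Timeline both arrive at 70 women in two years, which is exactly the target.

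**The concern.** The power statement counts every woman allocated, while another section of the same plan takes some women out between visits 1 and 2. The loss follows from a written rule; it is more than general dropout.

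Two of the three acupuncture sessions and four of the six planned urine collections (two at each of three visits) fall at visits 2 and 3. The urinary biomarkers are the primary outcome. If those visits show no difference, readers will judge the result against 0.80 power at d = 0.6, and the trial would be less sensitive than that. The plan also says its data will be used to size later proposals, so the sensitivity at the transfer visits should be stated correctly.

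**Working it through.** **Inputs from the plan:** n = 35 per group, two-sample t-test, d = 0.6, alpha 0.05, stated power 0.80. **Not in the plan:** the sidedness (both are tried) and the loss rate (10%, 20% and 30% are assumed, equal in both groups).

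**Formula.** With n analysed per group, the t statistic has 2n − 2 degrees of freedom and noncentrality d × √(n/2). Power is the probability that it passes the critical value.

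**Step 1: reproduce the stated figure.** For n = 35, the noncentrality is 0.6 × √17.5 = 2.51 on 68 degrees of freedom.

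- One-sided 5%: power 0.7996. This matches 0.80.
- Two-sided 5%: power 0.697. This does not match.

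The exact number needed for 0.80 is 35.04 per group one-sided and 44.6 two-sided. So the stated figure holds only one-sided, with every allocated woman analysed and no slack.

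**Step 2: smallest losses, one-sided.** With 34 per group power is 0.789, and with 33 it is 0.778. Two women lost per group cost about two percentage points.

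**Step 3: assumed losses at visits 2 and 3.** Numbers are rounded down to whole women: 35 × 0.90 = 31.5, taken as 31; 35 × 0.80 = 28; 35 × 0.70 = 24.5, taken as 24.

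| Assumed loss | n per group | Power at d = 0.6, one-sided | Power at d = 0.6, two-sided | d detectable with 80% power, one-sided | d detectable with 80% power, two-sided |
|---|---|---|---|---|---|
| 0% | 35 | 0.800 | 0.697 | 0.60 | 0.68 |
| 10% | 31 | 0.755 | 0.642 | 0.64 | 0.72 |
| 20% | 28 | 0.716 | 0.597 | 0.67 | 0.76 |
| 30% | 24 | 0.657 | 0.530 | 0.73 | 0.83 |

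**Step 4: is the loss made good elsewhere?** Projected recruitment is 70 cycles a year × 50% × 2 years = 70, so there is no surplus. No replacement is described. The restart provision covers poor response to initial stimulation, and the postponement provision covers the questionnaire only. Neither supplies visit-2 or visit-3 urine from a woman removed because embryos did not progress or transfer was cancelled.

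**The case against.** Several objections have weight.

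- **Not every disrupted cycle loses data.** A reader might infer that 35 per group can never be reached after visit 1. The documents do not support that: poor responders may restart, and the questionnaire survives a postponed transfer. The PSS is also the only endpoint that the Power analysis section puts in practical terms. The offsets are real but partial, and they do not reach the urine samples of removed women.
- **The size is unknown.** No cancellation rate is given, and nothing in the documents supports 10% as a starting point. The loss could be one woman per group, which costs about one percentage point. Only the direction is certain once any loss occurs.
- **No analysis visit is named.** A reader might infer that the plan commits to separate t-tests at visits 2 and 3. It does not. Aim 1 concerns change before and after acupuncture, and a woman removed after visit 1 has already given one such pair. What remains is that the power claim is attached to no visit and so would be read as covering all three.
- **Sidedness matters more than a modest loss.** Going from one-sided to two-sided lowers power from 0.80 to 0.70 with nobody lost; a 10% loss lowers the one-sided figure to 0.76. This is true, but settling the sidedness leaves the loss unaddressed.
- **It is a pilot.** That argues against asking for more women. It does not excuse a definite power figure that the plan's own removal rule undercuts.

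**Conclusion.** The point holds in a conditional form. The stated power of 0.80 at d = 0.6 requires all 35 women per group and a one-sided 5% test. Any removal between visits 1 and 2 puts visits 2 and 3 below it. Over an assumed loss of 10% to 30%, the shortfall from 0.80 is about 4 to 14 percentage points one-sided. On a two-sided test, power is about 16 to 27 points below 0.80, of which about 10 points come from sidedness alone.

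These sizes rest on the assumed rates, on equal loss in the two groups, and on a two-sample t-test at the visit in question.

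Two stronger readings should be avoided. A reader might infer that 0.80 is at least assured at visit 1; it is so only if the test is one-sided, which the plan does not say. A reader might also call this an arithmetic error. The stated figure does reproduce one-sided; the fault is an unstated assumption of no loss.

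**What to change.** In the Power analysis section:

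1. State whether the test is one-sided or two-sided, and which visit and endpoint the power refers to. Do not imply 0.80 at visit 1 unless the test is one-sided.
2. Restate power and detectable d at visits 2 and 3 for the number expected to reach transfer. Use the centre's own cancellation rate, or the 10% to 30% range above if none is available.
3. Specify one likelihood-based repeated-measures model for the three visits, so that women removed after visit 1 still contribute their visit-1 data.

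**Cost.** The text change is short, and the stated power becomes less favourable. The model adds some analysis work, since its outcome, covariance structure and handling of missing data must be written down. It assumes that data are missing at random, and it does not recover the lost visit-2 and visit-3 observations. No extra enrolment is needed, and no clinical procedure changes.

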#### *Control Group*

The participants in the comparison group will continue their current usual IVF care at the Center for Fertility and Reproductive Surgery. Participants in the control group will also be asked to attend three study visits. The first visit will take place between days 6-8 of the IVF cycle. The second visit will take place on the day of embryo transfer, prior to transfer. The third visit will take place post-embryo transfer but before the pregnancy test. This visit will occur within a windowed timeframe (48 hours post transfer, which includes anytime post-transfer on embryo transfer day) acknowledging the participant’s ability to return during that timeframe. At the beginning and end of each study visit, participants will provide a urine sample.

Study participants in this group will receive vouchers for 3 future acupuncture sessions, provided at no cost to them. These vouchers will be provided on the day of the participant’s embryo transfer, or mailed to them after embryo transfer, and may be used beginning 1 year from the date of the embryo transfer. In the event that embryo growth does not progress or implantation is cancelled for any reason, the subject’s participation in this study will end. For those subjects vouchers will be mailed to them after study visit 1 and will be valid beginning one year from study visit 1. The vouchers will then be valid for 1 year. (i.e., Control group embryo transfer on 6-1-15. Patient receives 3 acupuncture vouchers that are valid 6-1-16 through 6-1-17). The delayed use of the acupuncture vouchers is intended to avoid use of the acupuncture sessions during pregnancy in the control group which could potentially affect outcome data comparisons between the two groups. For the same reason, subjects will be asked to commit to abstaining from acupuncture for the same period of 1 year post-embryo transfer, should they be randomized to the control arm. In event of error, vouchers may be replaced by mailing new ones to the subject.

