#### *Determination of Stable Metabolites of Prostacyclin and Thromboxane in the Urine*

Urine samples will be collected from all study participants prior to and after each acupuncture session for the treatment group, and before and after each study visit for the control group. Stable metabolites of thromboxane and prostacyclin, 2, 3-dinor-TXB2 and 2, 3-dinor-6-keto-PGF1α, respectively will be determined on a later date. Specifically, a mid-stream urine sample will be collected in a sterile wide-mouth container. A 10mL aliquot will be centrifuged (300x g) for 10 min and the supernatant kept at -20C until assay. Stable metabolites of prostacyclin and thromboxane will be determined using ELISA kits according to the manufacturer’s protocol: TXB2 ELISA kit (Enzo Life Sciences, Inc., <http://www.biocompare.com/9956-Assay-Kit/1371009-TXBsub2sub-ELISA-kit/>), Urinary prostacyclin ELISA kit (Enzo Life Sciences, Inc., <http://www.enzolifesciences.com/ADI-900-025/urinary-prostacyclin-elisa-kit/>). The specification of the kit shows that both kits have fairly high sensitivity. The lowest detection limits for TXB2 and prostacyclin metabolites are 10.54pg/mL and 6.58pg/mL, respectively. We plan to perform preliminary tests to determine the appropriate dilution of the samples before assay. In case the concentrations are below the detection limits, samples will be concentrated using a Centricon® Filter Concentrator (Millipore Co.). In case the above method cannot increase the concentration to within detectable ranges, GC/MS methodology will be used– we will consult collaborators ([name], University of Houston) who determine prostacyclin and thromboxane metabolites using GC/MS on a routine basis.

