#### *Assessment of Self-Perceived Stress in Treatment and Control Group*

To determine whether acupuncture contributes to stress reduction, study participants in the treatment group will complete the Perceived Stress Scale (Cohen, 1983 see Addendum) to assess self-perceived stress cycle days 6 through 8 of ovarian stimulation, on the day of embryo transfer, pre-embryo transfer and post-embryo transfer, but before the

pregnancy test, within 48 hours of transfer. Participants in this group will complete this scale before and after their acupuncture treatment.

Study participants in the control group will complete the same Perceived Stress Scale questionnaire once during days 6 through 8 of ovarian stimulation, on the day of embryo transfer, pre-embryo transfer and post-embryo transfer, but prior to the pregnancy test, within 48 hours of transfer.. In the event that the embryo transfer must be postponed for clinical reasons, the post-treatment questionnaire will be performed 3 to 7 days after the oocyte retrieval.

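### Both arms give urine before and after every visit, but the only analysis named is an unadjusted two-sample t-test; adjusting for the pre-session sample is a nearly free gain in precision

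*Combined protocol and SAP*

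**What the plan says.** Under Power analysis, 35 women per group, alpha .05 and power .80 are said to detect d of 0.6 or more, "assuming the Student's T-test will be used to determine the differences between two independent samples". The only worked example there is the Perceived Stress Scale (PSS). Sidedness, the variable compared and the visit are not stated.

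The Project Abstract makes urine markers the main endpoint: "The primary outcome measures include prostacyclin and thromboxane vasoactive biomarkers". Aim 1 is "To measure the effects of acupuncture on key vasoactive urine molecules, i.e. prostacyclin and thromboxane, before and after acupuncture". Under Determination of Stable Metabolites, urine is taken "prior to and after each acupuncture session for the treatment group, and before and after each study visit for the control group". The Control Group section agrees: "At the beginning and end of each study visit, participants will provide a urine sample". A pre-session or pre-wait value is therefore planned for both arms at all three visits. Nothing in the text available for review uses it as a covariate.

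The PSS is collected differently. The abstract has it "administered before each acupuncture session for the study group, and before a 30-40-minute waiting period for the control group". The Assessment of Self-Perceived Stress section has the acupuncture arm complete it before and after each session, while controls "complete the same Perceived Stress Scale questionnaire once during days 6 through 8 of ovarian stimulation" and then at each of the two transfer-related visits.

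**The concern.** A two-sample t-test on post values ignores the pre sample. A t-test on change uses it, but with a fixed weight of 1. A model that estimates the weight does at least as well in almost all cases, and the data it needs are already planned. With 70 women, any precision given up matters.

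The choice is not neutral. If the pre-post correlation is below 0.5 and the SDs are equal, a change t-test, which is a natural reading of a before-and-after aim, has less power than ignoring the pre sample altogether.

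The right covariate also depends on the question. At visit 1 there is only one pre sample, taken before any acupuncture. At visits 2 and 3 the same-visit pre sample follows earlier sessions in the acupuncture arm, so adjusting for it answers a different question from adjusting for the visit-1 sample.

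**Working it through.** **Inputs.** From Power analysis: 35 per arm, d=0.6, alpha .05, power .80. Not in the documents: sidedness, the metabolite SDs and the pre-post correlation r. I use r=0.3, 0.5 and 0.7 as assumptions, with equal pre and post SDs, roughly normal data and a linear relation.

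**Reproducing the plan's figure.** The noncentrality is d·√(n/2) = 0.6·√17.5 = 2.510 on 68 df. One-sided .05 (critical value 1.668) gives power 0.800. Two-sided .05 (critical value 1.995) gives 0.697. The stated 80% is therefore reproduced as a one-sided test.

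**Comparing three analyses, with d in post-value SD units.**
- Post values: the SD is 1 and the effective d is 0.6, on 68 df.
- Change: the SD is √(2(1−r)) = 1.183/1.000/0.775, so the effective d is 0.507/0.600/0.775, on 68 df.
- Adjusted model (ANCOVA): the residual SD is √(1−r²) = 0.954/0.866/0.714, so the effective d is 0.629/0.693/0.840, on 67 df. Power is averaged over chance baseline imbalance, which inflates the variance by (N−3)/(N−4) = 67/66.

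| Two-sided .05 power | r=0.3 | r=0.5 | r=0.7 |
|---|---|---|---|
| t-test, post values | 0.697 | 0.697 | 0.697 |
| t-test, change | 0.552 | 0.697 | 0.891 |
| ANCOVA | 0.730 | 0.809 | 0.930 |

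One-sided, the post-value test gives 0.800, change gives 0.676/0.800/0.941 and ANCOVA gives 0.826/0.885/0.965. The ordering of ANCOVA over the other two does not depend on sidedness. Simulation with 20,000 trials at r=0.5 gave 0.699 (post), 0.691 (change) and 0.809 (ANCOVA).

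**Where adjustment stops helping.**
- Against post values, ANCOVA wins when (1−r²)·67/66 < 1, that is r > 1/√67 = 0.122. With 30, 25 or 20 per arm, 1/√(N−3) is 0.132, 0.146 or 0.164.
- At r=0 and d=0.6, ANCOVA has 0.690 against 0.697 with 35 per arm, a loss of 0.7 points. With 20 per arm it has 0.446 against 0.456, a loss of 1.0 point.
- Against change, ANCOVA wins when (1+r)·67/66 < 2, that is r < 0.970. Above that, change leads by at most about 0.4 points in the cases run (d=0.1, r=0.99: 0.831 against 0.827).

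**If d=0.6 is in change-score SD units instead.** The change t-test then has 0.697 at every r. The effect in post-value units is 0.6·√(2(1−r)), and ANCOVA has 0.759/0.735/0.712 at r=0.7/0.8/0.9 (0.861/0.809 at r=0.3/0.5).

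**The case against.** The strongest reply is that nothing has been committed to that needs replacing. The t-test is a power assumption, its only worked example is the PSS, and neither it nor d=0.6 is tied to a urine marker. A t-test after randomisation is also valid. All of this stands. A reader might infer that the plan prescribes a wrong test for its primary outcome, and the documents do not support that.

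The size of the gain is also open to challenge. It depends on a correlation the documents do not give and on which SD defines d. In change-score units with r between 0.7 and 0.9, the gain over a change t-test is only about 1.5 to 6 points. This stands too, so the figures are illustrative.

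Attrition matters as well. Under Removal from study, participation ends if transfer is cancelled, so fewer than 70 may be analysed at visits 2 and 3. That moves the threshold to 0.13–0.16 at 30 to 20 per arm, which is still a low correlation.

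Two further inferences fail:
- A reader might think that an unfixed covariate would leave the pilot unable to inform later sample sizes. The Study Data section records urine results with dates and times, so SDs and pre-post correlations can be calculated whichever test is used.
- A reader might think that a log scale is required. The documents give no distribution for the metabolites, so the scale is for the sponsor to choose.

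**Conclusion.** The point holds as a free improvement and does not show an error in the plan. Adjusting for a pre sample already collected in both arms gives more power than a post-value t-test once r exceeds about 0.12 with all 70 analysed. It also gives more power than a change t-test on the same pre sample, unless r is above about 0.97 with equal SDs, where the loss is trivial. At r=0.5 and d=0.6 in post-value SD units, two-sided power rises from 0.70 to 0.81.

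These comparisons are cleanest at visit 1. At visits 2 and 3, if earlier sessions carry over, the three analyses estimate different quantities and the 0.12 threshold need not apply.

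The urine argument does not transfer directly to the PSS. Controls have no end-of-visit score, so only pre-session scores can be compared like for like.

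**What to change.** For each primary urine metabolite, compare arms with a linear model of the post-session or post-wait value on randomised arm, adjusted for the pre-session or pre-wait value. Choose the measurement scale before the data are compared by arm.

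Match the covariate to the question:
- For the total effect of acupuncture to date, use the visit-1 pre sample. For a woman who returns after a cancelled stimulation (Poor Response to Egg Retrieval), use her first visit-1 pre sample, because a repeated one may follow acupuncture.
- For a within-session effect, use the same-visit pre sample. At visits 2 and 3 this estimates only the added effect of that session.

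For the PSS, compare pre-session scores at visits 2 and 3 between arms, adjusted for the visit-1 pre-session score. The scale asks about the last month, so the recall windows overlap and any effect may be diluted.

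The cost is a change of analysis wording and one degree of freedom, with no new samples or visits. If the pre sample turns out nearly unrelated to the outcome, the loss is at most about one point of power at 20 or more per arm.

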#### **Inclusion criteria:**

Women between ages 21-42 years seeking IVF. Participants must be willing to undergo acupuncture and have no contraindications to needle insertion.

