**Norm Table for the PSS 10 item inventory**

Category	N	Mean	S.D.
Gender			
Male	926	12.1	5.9
Female	1406	13.7	6.6
Age			
18-29	645	14.2	6.2
30-44	750	13.0	6.2
45-54	285	12.6	6.1
55-64	282	11.9	6.9
65 & older	296	12.0	6.3
Race			
white	1924	12.8	6.2
Hispanic	98	14.0	6.9
black	176	14.7	7.2
other minority	50	14.1	5.0

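### The 1.5-point PSS difference comes from using a standard deviation of 6.2 as a variance, and 80% power at d = 0.6 holds only for a one-sided test that the plan never declares

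*Combined protocol and SAP*

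**What the plan says.** The Power analysis section takes 35 patients per group and a Student's t-test for two independent samples. It states that standardised effects of 0.6 or more "will be found statistically significant with alpha .05 and power .80". Neither this section nor any other says whether the test is one- or two-sided.

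The section then converts the effect to PSS points. It says that "the PSS validation samples showed a mean about 13.5 with variance=6.2" and concludes that "only averaged differences greater than 1.5 raw score points in PSS will be found statistically significant".

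The Addendum reproduces the norm table for the 10-item PSS. Its column heading is "Category N Mean S.D". The two age rows relevant to this trial are "18-29 645 14.2 6.2" and "30-44 750 13.0 6.2", and the row for women is "Female 1406 13.7 6.6". The inclusion criterion is "Women between ages 21-42 years seeking IVF", so those two age bands cover the whole eligible range.

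**The concern.** Three things looked wrong in two sentences.

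- **The spread of the PSS.** The power section calls 6.2 a variance, while the Addendum puts the same number in the S.D. column. If the table is right, the 1.5 points is far too small.
- **Sidedness.** The sample size, effect size, alpha and power cannot be checked without knowing the sidedness, and they do not agree under the usual two-sided 5% test.
- **Threshold or detectable effect.** The second sentence presents a difference that the study has 80% power to detect as the smallest difference that can reach significance. These are different quantities.

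The PSS sentence is the only place where the plan gives its sensitivity in practical units, and psychological well-being is one of the two Specific Aims. A reader who believes that 1.5 points is within reach could take a null PSS result as evidence against a stress effect that the study would probably have missed.

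**Working it through.** **Inputs.** n = 35 per group, d = 0.6, alpha 0.05, power 0.80, variance 6.2 and 1.5 points (Power analysis); S.D. 6.2 for ages 18–29 and 30–44, and 6.6 for women (Addendum norm table). All 35 per group are taken as evaluable.

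**Step 1: the power statement.** Power comes from the noncentral t distribution with 68 degrees of freedom and noncentrality d × √(n/2) = 0.6 × √17.5 = 2.51.

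| | One-sided 5% | Two-sided 5% |
|---|---|---|
| Power at d = 0.6 | 0.7996 | 0.6965 |
| d with 80% power | 0.600 | 0.679 |
| Smallest observed d that is significant, t × √(2/35) | 0.399 | 0.477 |

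The plan's figures reproduce one-sided and not two-sided. A paired or one-sample test with n = 35 gives 97% (one-sided) or 93% (two-sided), so that does not explain the 0.80 either.

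**Step 2: the plan's 1.5 points.** 0.6 × √6.2 = 0.6 × 2.49 = 1.494. The figure therefore uses 6.2 as a variance. (6.2 × √(2/35) = 1.48 is also close to 1.5, but that is the standard error of the difference, not a detectable difference, and the plan itself says variance.)

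**Step 3: what 6.2 is.** Combining the two age bands gives a mean of (645 × 14.2 + 750 × 13.0)/1395 = 13.55, which matches the plan's mean of about 13.5. The combined S.D. is √(6.2² + 0.462 × 0.538 × 1.2²) = 6.23. So both numbers in the power section match this table, with 6.2 as an S.D. No S.D. in the table is below 5.0; an S.D. of 2.49 appears nowhere.

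**Step 4: PSS difference with 80% power.**

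| S.D. | One-sided | Two-sided |
|---|---|---|
| 6.2 | 0.6004 × 6.2 = 3.72 | 0.6794 × 6.2 = 4.21 |
| 6.6 (women) | 0.6004 × 6.6 = 3.96 | 0.6794 × 6.6 = 4.48 |

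Relative to the stated 1.5 with S.D. 6.2: 3.72/1.5 = 2.5 and 4.21/1.5 = 2.8.

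**Step 5: power for a true 1.5-point difference.**

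| S.D. | d = 1.5/S.D. | One-sided | Two-sided |
|---|---|---|---|
| 5.0 (lowest in table) | 0.300 | 0.34 | 0.24 |
| 6.2 | 0.242 | 0.26 | 0.17 |
| 6.6 (women) | 0.227 | 0.24 | 0.16 |
| 7.2 (highest in table) | 0.208 | 0.22 | 0.14 |

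**Step 6: the literal reading.** Suppose the sentence means the smallest observed difference that reaches significance. With S.D. 6.2 that is 0.399 × 6.2 = 2.47 one-sided or 0.477 × 6.2 = 2.96 two-sided. Even with the mistaken S.D. of 2.49 it would be 0.99 or 1.19. No version of this reading gives 1.5.

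**The case against.** **On sidedness,** the power statement contains no contradiction: read as one-sided, its four figures agree. No section says two-sided, so what can be shown is an omission, not a wrong number. The documents also point both ways. Hypothesis and Specific Aims asks, without direction, whether acupuncture affects the molecules. The stress assessment section speaks of stress reduction, and the section on significance or innovation expects raised vasoactive biomarkers and/or lower perceived stress. This largely stands: the 0.80 is wrong only if the test is two-sided. The last phrase does not settle the biomarker test, however, because prostacyclin and thromboxane act in opposite directions and a rise in both has no single meaning.

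**On the PSS figure,** four points can be made.

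- The power section refers to validation samples and the Addendum to norms, so the link is inferred. It is nevertheless strong, since the mean and the 6.2 both match.
- The S.D. in IVF patients is not in the documents and may differ from that of a general US sample. This is true, but over every S.D. in the table the power at 1.5 points stays between 14% and 34%.
- Baseline adjustment could lower the detectable difference. To reach 1.5 points it would need a baseline correlation of about 0.92 one-sided or 0.93 two-sided, and the plan assumes a plain two-sample test.
- PSS is a secondary outcome in a pilot, the sample size was not derived from the 1.5 points, and future sample sizes are to use the pilot's own data. This limits the seriousness but does not make the figure right.

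**The confusion of threshold and detectable difference** is mainly one of wording, and correcting the sentence removes it.

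**Conclusion.** The concern holds. The 1.5-point figure is wrong under either sidedness and under either reading of the sentence. With S.D. 6.2, the study can detect 4.2 points two-sided or 3.7 one-sided with 80% power (4.5 or 4.0 with the women's S.D. of 6.6), and its power at 1.5 points is 17% or 26%.

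The power statement is incomplete. It is correct for a one-sided 5% test; for a two-sided test, power at d = 0.6 is 70% and 80% power needs d = 0.68. The documents do not settle which was meant.

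These results assume that the norm-table S.D. applies to the trial population and that all 35 women per group are evaluable. The error should be corrected because it affects how a null stress result would be read. It does not undermine the design.

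**What to change.** Restate the two sentences. For the primary biomarker question, which is worded without direction, a two-sided test is the natural choice. Suggested text:

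*With 35 evaluable women per group, a two-sided 5% t-test has 80% power to detect d = 0.68 (70% power at d = 0.6). Taking an S.D. of 6.2 from the PSS norm table, this is a difference of about 4.2 points (4.5 with the S.D. of 6.6 for women).*

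If a one-sided test was intended, say so explicitly, keep d = 0.6, and give about 3.7 points (4.0 with S.D. 6.6).

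In either case:

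- replace the word variance with S.D. Changing the word alone is not enough, because the 1.5 was calculated from it;
- describe the result as a difference detectable with 80% power, not as a significance threshold;
- state that the figures assume all 35 per group are evaluable, given that the Removal from study section ends participation when embryo growth fails or the transfer is cancelled.

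The cost is two rewritten sentences and a less favourable stated sensitivity: 4.2 points (3.7 one-sided) instead of 1.5, and d = 0.68 instead of 0.6 if two-sided. Enrolment, visits and assays do not change.
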